- 3) Have experienced heavy menstrual bleeding associated with fibroids (AUB-L) for at least the previous three months as reported by the subject
- 4) Have ≥ 1 and ≤ 10 fibroids of FIGO types 1, 2, 3, 4, and/or type 2-5, with diameter ≥ 1.0 cm and ≤ 5.0 cm as determined by credentialed transvaginal sonography or magnetic resonance imaging (MRI). Fibroids of type 5, 6, and 7 do not count toward the clinically relevant total, irrespective of size.
- 5) Have at least one type 1, type 2, type 3, or type 2-5 fibroid.
- 6) Pictorial blood loss assessment chart (PBAC) score ≥ 150 and ≤ 500 during a single baseline cycle
- 7) Consistent menstrual cycles of between 22 to 35 days in duration that meet the following requirements for at least 4 of the last 6 menstrual cycles prior to enrollment as reported by the subject:
 - (1) Variations in cycle length of no more than ± 4 days, and
 - (2) Bleeding duration of 3-10 days, in which the bleeding requires use of more than a pantiliner
- 8) Subject is not at material risk for pregnancy (not sexually active; has been sterilized; does not have a male partner or is in a monogamous relationship with a sterilized male partner; reliably uses barrier contraception, or oral or vaginal hormonal contraception. Subject is willing to maintain use or non-use of non-injectable hormonal contraception uniformly from 6 months pre-study through the 12-month follow-up period.¹ If a subject is on oral/vaginal hormonal contraception solely for bleeding control, or if a subject does not wish to commit to 12 months of consistent hormonal contraceptive use, subject must discontinue use as per the washout period specified in Appendix H.
- 9) Speaks and reads a language for which validated questionnaires are available
- 10) Willing and able to read, understand, and sign the informed consent form, to participate in the study and to adhere to all study follow-up requirements

¹ If changes in medical insurance would require a change in birth control preparation, then the study sponsor will provide the oral contraceptives taken at study enrollment free of charge until the one-year follow-up visit is completed.

Exclusion Criteria

- 1) Pregnancy, as determined by urine or serum hCG obtained within 24 hours prior to treatment with Sonata
- 2) Urgent need for surgery to treat fibroid symptoms
- 3) Desire for current or future childbearing
- 4) Presence of a tubal implant for sterilization
- 5) Postmenopausal by history

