12.1 Screening / Baseline Phase

A. Candidate Identification

All patients at the Investigational Sites with a complaint of HMB will be asked about their interest in study participation. For those patients who express an interest to participate, the inclusion/exclusion criteria will be reviewed against existing medical history and the results of any standard clinical work-up to assess preliminary eligibility. Additionally, subjects may be recruited from site catchment area.

If the patient is not excluded on the basis of existing medical history and standard clinical work-up, the patient will be asked to provide informed consent to participate in the study. Before being asked to sign the informed consent form, patients will be given adequate time to consider the potential risks and benefits of study participation, as well as the study's follow-up schedule of 36 months and study requirements to complete various questionnaires and undergo various evaluations. If the patient understands the risks and benefits, and still wishes to participate, she will be asked to sign the informed consent form.

B. Final Screening/Baseline Assessments

Screening assessments include the following as shown in Table 3

- Demographics
- Medical / surgical history, including pregnancy history (prior pregnancies, live birth, c-section) and previous fibroid treatment (surgery, UAE, MRgFUS, GnRH-a, SPRM)
- Interview regarding hemostasis and menstrual history
- Vital signs (including temperature, pulse, blood pressure, height, weight), pelvic exam, and cervical cancer evaluation
- Endometrial biopsy
- Transvaginal ultrasound (TVUS)
- Saline-infused sonohysterography (SIS) or hysteroscopy is optional for further assessment of the endometrial cavity if needed to assess suspicion of intracavitary mass or significant intrauterine synechiae.
- Blood test (hemoglobin, serum creatinine)
- Cervical gonorrhea (GC) and chlamydia testing
- Urine or serum hCG
- UFS-QOL Questionnaire - to be completed with consideration to symptoms experienced during the last three menstrual cycles.
- EQ-5D Questionnaire - to be completed with consideration to symptoms experienced during the first full day of bleeding during the menstrual cycle in which the subject completes the Menstrual diary (PBAC).

- WPAI :SHP Questionnaire – to be completed with consideration to symptoms experienced during the last 28 days (most recent menstrual cycle)
 - Concomitant medications

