12.3 Follow-up Phase

- A. Follow-up visits will occur in accordance with Table 6 below. The day of the Sonata treatment represents Day 0. Study visits that do not occur within the below time windows will be considered protocol deviations.

Table 6 Follow-up (FU) Visit Windows

Visit	Allowed Visit Date Range
FU Visit 1 - 10 days	± 4 days
FU Visit 2 - 30 days	± 1 week
FU Visit 3 - 3 months	± 2 weeks
FU Visit 4 - 6 months	± 4 weeks
FU Visit 5 - 12 months	± 2 months
FU Visit 6 - 2 years	± 2 months
FU Visit 7 - 3 years	± 2 months

- B. The measurements and evaluations that will occur at each follow-up visit are provided below.

- 1) Follow-up Visit 1: 10 Days (± 4 days)
(Phone Call or visit at Investigator's discretion)

(a) Adverse Events

The primary purpose of Follow-up Visit #1 is to assess safety. Subjects will be asked if they have experienced any untoward medical occurrences since the Sonata treatment. If so, these events will be recorded on the Adverse Event case report form, in accordance with the procedures outlined later in this protocol.

(b) Post-treatment follow up

Subjects will be asked whether there is any change to their medical status. Subjects will be asked specifically if they have experienced any signs or symptoms of fibroid shedding: cramping, bleeding, passage of any tissue per vaginam.

(c) Concomitant Medications

Subjects will be asked about concomitant medications, noting in particular concomitant medications taken for the treatment of HMB.

(d) Adherence with/Continuance of Birth Control Method

Subjects will be asked if they are adhering to their chosen method of birth control, and if there have been any changes in their birth control method, including changes to medication type and preparation.

2) Follow-up Visit #2: 30 Days (\pm 1 week)

(a) Adverse Events

Subjects will be asked if they have experienced any untoward medical occurrences since the Sonata treatment. If so, these events will be recorded on the Adverse Event case report form, in accordance with the procedures outlined later in this protocol.

(b) Return to Normal Daily Activity

Subjects will be asked to submit their completed Treatment Recovery Questionnaire (Appendix C). Subjects who are not back to normal activity will be followed up by phone visits weekly until the subject has resumed normal activity or the reason for not resuming normal activity is not expected to change.

(c) Surgical Reintervention

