Subjects will be asked if they have undergone any surgical procedure to treat their heavy menstrual bleeding. If so, the procedure performed and the date of the reintervention will be recorded.

(d) Concomitant Medications

Subjects will be asked about concomitant medications, noting in particular concomitant medications taken for the treatment of HMB.

(e) Pregnancy/Pregnancy Outcomes

Subjects will be asked if they have become pregnant since the last follow-up visit. If so, the subject will be released from all protocol specified follow-up assessments and visits, however the subject will be followed and pregnancy outcomes (including any complications) will be recorded as described in Section 10.6 of this protocol.

(f) Post-treatment follow up

Subjects will be asked whether there is any change to their medical status. Subjects will be asked specifically if they have experienced any signs or symptoms of fibroid shedding: cramping, bleeding, passage of any tissue per vaginam.

(g) Adherence with/Continuance of Birth Control Method

Subjects will be asked if they are adhering to their chosen method of birth control, and if there have been any changes in their birth control method, including changes to medication type and preparation.

Note: During follow-up visit #2, the subject will be given study materials in anticipation of follow-up visit #3, which will be comprised of the following:

- a copy of the EQ-5D Questionnaire (Appendix A). The EQ-5D should be completed during the subject's 3rd menstrual cycle post-treatment, preferably on the first full day of bleeding. It should be completed based solely on symptoms from that cycle.
- Menstrual diary (PBAC) with completion instructions noting that only the sanitary products provided should be used during the study while completing the PBAC.
- A supply of sanitary products in sufficient quantity to cover use for one menstrual cycle for the completion of the PBAC.

3) Follow-up Visit #3: 3 Months (\pm 2 weeks)

(a) UFS-QOL, EQ-5D, and WPAI:SHP Questionnaires

Subjects will be asked to return their completed EQ-5D questionnaire and will be asked to complete the UFS-QOL and WPAI:SHP questionnaires.

(b) Menstrual Diary

Subjects will be asked to return their completed menstrual diary (PBAC) for the menstrual cycle preceding the visit.

(c) Adverse Events

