Subjects will be asked if they have experienced any untoward medical occurrences since the Sonata treatment. If so, these events will be recorded on the Adverse Event case report form, in accordance with the procedures outlined later in this protocol.

(d) Surgical Reintervention

Subjects will be asked if they have undergone any surgical procedure to treat their heavy menstrual bleeding. If so, the procedure performed and the date of the reintervention will be recorded.

(e) Pregnancy/Pregnancy Outcomes

Subjects will be asked if they have become pregnant since the last follow-up visit. If so, the subject will be released from all protocol specified follow-up assessments and visits, however the subject will be followed and pregnancy outcomes (including any complications) will be recorded as described in Section 10.6 of this protocol.

- (f) Amenorrhea
If the subject becomes amenorrheic, a pregnancy test (urine or serum hCG) will be performed and, if negative, a serum FSH level determination will also be obtained
- (g) Concomitant Medications
Subjects will also be asked about concomitant medications, noting concomitant medications taken for the treatment of excessive uterine bleeding.
- (h) Post-treatment follow up
Subjects will be asked whether there is any change to their medical status. Subjects will be asked specifically if they have experienced any signs of fibroid shedding: cramping, bleeding, passage of any tissue per vaginam.
- (i) Adherence with/Continuance of Birth Control Method
Subjects will be asked if they are adhering to their chosen method of birth control, and if there have been any changes in their birth control method, including changes to medication type and preparation.

Note: During follow-up visit #3, the subject will be given study materials in anticipation of follow-up visit #4, which will be comprised of the following:

- A copy of the EQ-5D Questionnaire (Appendix A). The EQ-5D should be completed during the subject's 6th menstrual cycle post-treatment, preferably on the first full day of bleeding. It should be completed based solely on symptoms from that cycle. If the subject has become amenorrheic, the EQ-5D may be completed at any time during the follow-up visit window.
- Menstrual diary (PBAC) with completion instructions noting that only the sanitary products provided should be used during the study while completing the PBAC.

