- A supply of sanitary products in sufficient quantity to cover use for one menstrual cycle for the completion of the PBAC.

- 4) Follow-up Visits #4-5: 6 Months (\pm 4 weeks) and 12 Months (\pm 2 Months)
- (a) MRI (12 months only)
 - (b) UFS-QOL, EQ-5D, and WPAI:SHP Questionnaires
Subjects will be asked to return their completed EQ-5D questionnaire and will be asked to complete the UFS-QOL and WPAI:SHP questionnaires.
 - (c) Menstrual Diary
Subjects will be asked to return their completed menstrual diary (PBAC) for the menstrual cycle preceding the visit.
 - (d) Adverse Events
Subjects will be asked if they have experienced any untoward medical occurrences since the Sonata treatment. If so, these events will be recorded on the Adverse Event case report form, in accordance with the procedures outlined later in this protocol.
 - (e) Surgical Reintervention
Subjects will be asked if they have undergone any surgical procedure to treat their heavy menstrual bleeding. If so, the procedure performed and the date of the reintervention will be recorded.
 - (f) Pregnancy/Pregnancy Outcomes
Subjects will be asked if they have become pregnant since the last follow-up visit. If so, the subject will be released from all protocol specified follow-up assessments and visits, however the subject will be followed and pregnancy outcomes (including any complications) will be recorded as described in Section 10.6 of this protocol.
 - (g) Post-treatment follow-up
Subjects will be asked whether there is any change to their medical status. Subjects will be asked specifically if they have experienced any signs of fibroid shedding: cramping, bleeding, passage of any tissue per vaginam.
 - (h) Amenorrhea
If the subject becomes amenorrheic, a pregnancy test (urine or serum hCG) will be performed and, if negative, a serum FSH level determination will also be obtained.
 - (i) Concomitant Medications
Subjects will also be asked about concomitant medications, noting concomitant medications taken for the treatment of excessive uterine bleeding.

(j) Subject Satisfaction

Subjects will be asked to rate their satisfaction with the treatment, with responses based on a 6-point Likert scale ranging from “very satisfied” to “very dissatisfied”. They will also be asked if they would recommend the treatment to a friend with the same health problems using a 4-point scale from “definitely yes” to “definitely not”.

(k) Overall Treatment Effect (OTE)

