Subjects will be asked to indicate whether their uterine fibroid symptoms have improved, remained the same, or worsened. If the subject indicates that her symptoms have improved, she will be asked to rate the degree of improvement on a 7-point scale from “almost the same, hardly better at all” (1) to “a very great deal better” (7). If the subject indicates that her symptoms worsened, she will be asked to rate the degree of worsening on a 7-point scale from “almost the same, hardly worse at all” (-1) to “A very great deal worse” (-7).

(l) Adherence with/Continuance of Birth Control Method

Subjects will be asked if they are adhering to their chosen method of birth control, and if there have been any changes in their birth control method, including changes to medication type and preparation.

Note: During follow-up visit #4, the subject will be given study materials in anticipation of follow-up visit #5, which will be comprised of the following:

- A copy of the EQ-5D Questionnaire (Appendix A). The EQ-5D should be completed during the subject’s 12th menstrual cycle post-treatment, preferably on the first full day of bleeding. It should be completed based solely on symptoms from that cycle. If the subject has become amenorrheic, the EQ-5D may be completed at any time during the follow-up visit window.
- Menstrual diary (PBAC) with completion instructions noting that only the sanitary products provided should be used during the study while completing the PBAC.
- A supply of sanitary products in sufficient quantity to cover use for one menstrual cycle for the completion of the PBAC.

- 5) Follow-up Visit 6 and 7: 2 and 3 years
(Phone Call or mail at Investigator's discretion)
- (a) UFS-QOL, EQ-5D, and WPAI:SHP Questionnaires
Subjects will be asked to return their completed EQ-5D questionnaire and will be asked to complete the UFS-QOL and WPAI:SHP questionnaires.
- (b) Pregnancy/Pregnancy Outcomes
Subjects will be asked if they have become pregnant since the last follow-up visit. If so, the subject will be released from any remaining protocol specified follow-up assessments and visits, however the subject will be followed and pregnancy outcomes (including any complications) will be recorded as described in Section 10.6 of this protocol.
- (c) Adverse Events

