5.5.2.5 EuroQOL EQ-5D

The EQ-5D should be completed during the subject’s 3rd, 6th, and 12th menstrual cycles post-treatment, preferably on the first full day of bleeding. It should again be completed at 2 years and at 3 years post-treatment. It should be completed based solely on symptoms from that cycle. If the subject has become amenorrheic, the EQ-5D may be completed at any time during the follow-up visit window.

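### Follow-up EQ-5D is timed by cycle number but visits and PBAC by calendar, so for women with short cycles the 12-month score can predate the 12-month window and often describes a different cycle from the PBAC

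*Protocol*

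**What the plan says.** **Follow-up EQ-5D.** The notes in Protocol 12.3 on materials handed out at visits 2, 3 and 4 place the form in the "3rd menstrual cycle post-treatment, preferably on the first full day of bleeding", the "6th menstrual cycle post-treatment, preferably on the first full day of bleeding" and the "12th menstrual cycle post-treatment, preferably on the first full day of bleeding". SAP 5.5.2.5 gives the same cycle numbers and adds: "It should be completed based solely on symptoms from that cycle". For the 6- and 12-month forms, women who have become amenorrheic may instead complete the form at any time in the visit window. No such link to the window is given for menstruating women.

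**Visits.** Protocol 12.3 and Table 6 set calendar windows: 3 months ± 2 weeks, 6 months ± 4 weeks, 12 months ± 2 months. "The day of the Sonata treatment represents Day 0".

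**Follow-up PBAC.** Protocol 12.3: "Subjects will be asked to return their completed menstrual diary (PBAC) for the menstrual cycle preceding the visit". The PBAC is therefore anchored to the visit.

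**Baseline.** Protocol 12.1 B asks the woman to consider her symptoms during "the first full day of bleeding during the menstrual cycle in which the subject completes the Menstrual diary (PBAC"). At baseline the two instruments refer to one cycle.

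**Cycle length.** Inclusion criterion 7 (Protocol 4 L; SAP 5.2.1): "Consistent menstrual cycles of between 22 to 35 days in duration", for at least 4 of the last 6 cycles before enrolment.

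**Use.** SAP 5.6.4.2 lists the change in EQ-5D from baseline to 12 months as one of six secondary endpoints, summarized descriptively. SAP 5.6.8.2 makes no imputation for missing secondary data.

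**The concern.** A cycle number and a calendar date cannot agree across cycles of 22 to 35 days. A woman who follows the instruction may complete the form well before the window opens, rate only that cycle, and hand it in later as her 12-month result. The time point behind the endpoint then depends on her cycle length. The EQ-5D is alone in this: in Protocol 12.3 the UFS-QOL and WPAI:SHP are completed when she attends.

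The link between EQ-5D and PBAC that exists at baseline is also not carried into follow-up, so the two results filed under one visit may describe different cycles. Neither document says how an EQ-5D completed before the window is handled.

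**Working it through.** The plan gives no figure to reproduce, so this is date arithmetic.

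**Inputs from the documents:** Day 0 is treatment; cycle length L is 22 to 35 days; named cycles n = 3, 6, 12; windows as in Table 6. With a month of 30.44 days the windows are:
- 3 months: 91.3 ± 14 = day 77.3 to 105.3
- 6 months: 182.6 ± 28 = day 154.6 to 210.6
- 12 months: 365.25 ± 60.9 = day 304.4 to 426.1

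**Assumptions, not in the documents:** cycle length is constant after treatment; treatment falls at a random point in the cycle; the woman still menstruates; the first full bleeding day is the start of the bleed.

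**Step 1: start of the n-th bleed.** The first bleed starts U days after Day 0, with U between 0 and L, so bleed n starts on day (n − 1)L + U, between (n − 1)L and nL.

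| L (days) | 3rd bleed | 6th bleed | 12th bleed |
|---|---|---|---|
| 22 | 44–66 | 110–132 | 242–264 |
| 25 | 50–75 | 125–150 | 275–300 |
| 28 | 56–84 | 140–168 | 308–336 |
| 35 | 70–105 | 175–210 | 385–420 |

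**Step 2: thresholds.** At 12 months all starts precede the window if 12L < 304.4 (L < 25.4), some if 11L < 304.4 (L < 27.7), and none otherwise. None falls after the window closes. At 6 months: all if L < 154.6/6 = 25.8, some up to 154.6/5 = 30.9. At 3 months: all if L < 77.3/3 = 25.8, and some at every eligible length.

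At L = 28 the shares before the window are (77.3 − 56)/28 = 76%, (154.6 − 140)/28 = 52%, and 0% at 12 months. At L = 35 they are (77.3 − 70)/35 = 21%, 0% and 0%. At L = 22 with a visit on day 365, the 12th bleed began 365 − 264 = 101 to 365 − 242 = 123 days earlier.

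**Step 3: averages over assumed cycle lengths** (simulated; normal distributions truncated to 22–35 days). Entries are % at 3 / 6 / 12 months. The last column is the share whose 12th bleed starts after day 365.

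| Distribution of L | Before window, preferred day | Before window, last day of named cycle | EQ-5D and PBAC in different cycles, visit on nominal date | 12th bleed after day 365 |
|---|---|---|---|---|
| Uniform 22–35 | 69 / 48 / 35 | 7 / 14 / 18 | 8 / 33 / 64 | 25 |
| Normal(27, 2) | 84 / 68 / 40 | 4 / 8 / 10 | 0 / 12 / 52 | 1 |
| Normal(28, 2) | 76 / 53 / 24 | 2 / 3 / 4 | 1 / 7 / 37 | 4 |
| Normal(28, 3) | 74 / 52 / 30 | 4 / 8 / 10 | 3 / 16 / 48 | 11 |
| Normal(29, 3) | 68 / 41 / 20 | 2 / 4 / 6 | 5 / 15 / 43 | 17 |

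The different-cycle column counts a mismatch only if the EQ-5D cycle differs from the PBAC cycle under both readings of the cycle preceding the visit: the most recent bleed, or the last completed cycle.

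**Step 4: the opposite direction.** The 12th bleed can start after day 365 once 12L > 365.25, that is, L > 30.4. On day 365 a woman is at bleed 16–17 if L = 22, 13–14 if L = 28 and 10–11 if L = 35. In the last case her 12th cycle has not begun, and the form is not yet due at a visit on the nominal date.

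**The case against.** - **The first bleeding day is only preferred.** The form may be completed at any time in the named cycle, and late completion cuts the 12-month share to about 4–18%. This stands as a range. The preferred day is still the one the plan asks for.
- **The windows absorb much of the drift.** For cycles of 26 to 35 days the named cycle overlaps the window at all three visits, so a visit could often be timed to make the cycles match. That is true, but no instruction schedules visits by cycle number. With visit dates spread evenly over the window instead of on the nominal date, the 12-month mismatch is about 57–66%.
- **The windows govern visit dates.** A form dated before the window is not a stated deviation. This stands; the issue is what the score represents.
- **Unseen material.** The completion instructions in the appendices are only listed in the supplied text, so a completion date may already be captured.

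A reader might go further in four ways that the documents do not support:
- That most 12-month scores are early. A 28-day cycle gives none on the preferred day.
- That EQ-5D and PBAC come apart at all three visits. At 3 months mismatch is 0–8%, and the SAP schedule (Table 2) has no 3-month PBAC, although the protocol's Table 4 does.
- That 3-month scores are distorted by early recovery or fibroid shedding. No duration of shedding is given, and the SAP plans no joint EQ-5D and PBAC analysis that mismatch would spoil.
- That the baseline form must be completed on the first bleeding day. Protocol 12.1 B makes that day the reference for symptoms, not the completion date.

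**Conclusion.** The point holds as a timing defect of limited consequence. Protocol and SAP agree on the cycle-count rule, but it does not reliably deliver the 12-month time point that the SAP names, and it drops the baseline link to the PBAC cycle.

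The thresholds of 25.4 and 27.7 days follow from the windows, given constant cycles. The population shares before the window on the preferred day (20–40% at 12 months, 41–68% at 6, 68–84% at 3) and the mismatch shares (37–64%, 7–33%, 0–8%) also rest on assumed cycle-length distributions. The 22 to 35 days is a pre-enrolment criterion, and nothing is stated about cycles after treatment. The error runs both ways: short cycles give early scores, and cycles above about 30 days may leave the form not yet due at a visit on the nominal date, with no imputation if it is then missing. The EQ-5D is a descriptive secondary endpoint, and neither co-primary endpoint nor the sample size depends on it.

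**What to change.** In the Protocol 12.3 notes at visits 2, 3 and 4, and in SAP 5.5.2.5:

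1. Replace the 3rd, 6th and 12th cycle with the cycle in which the PBAC for that visit is completed, keeping the first full bleeding day as the preferred day.
2. If a replacement PBAC is required because study products were not used (Protocol 12.1 F), repeat the EQ-5D in the replacement cycle.
3. Keep the existing rule for amenorrheic women. For a 3-month visit without a PBAC, use the cycle preceding the visit, and reconcile the two schedules on whether a 3-month PBAC is collected.
4. Record the EQ-5D completion date, if it is not already captured, so that out-of-window forms can be identified.

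This removes the cycle mismatch by construction and makes EQ-5D timing follow the visit at any cycle length. A form may still predate a visit held early in its window, but by no more than about two cycles.

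Cost: wording in the protocol, SAP and subject instructions, site retraining, and some loss of comparability with forms already collected. No visit or new form is added; a repeat EQ-5D is needed only where a PBAC is replaced.
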